6.5.5 Study Variables and Key Endpoints

For specific aim 1, we will assess the concordance between prostate MRI and PSMA-PET/MRI for the detection of seminal vesicle invasion and pelvic metastatic disease. The total number of pelvic nodal metastases detected on MRI and PSMA-PET/MRI will be compared. The confidence in detection of seminal vesicle invasion on a 0-3 Likert scale will also be compared between MRI and PSMA-PET/MRI. The primary endpoint for specific aim 1 number of patients who demonstrate pelvic LN metastases on PSMA-PET/MRI that were not detected on conventional anatomic imaging. We expect at least 25% of patients to demonstrate pelvic LN metastases that were not detected on conventional anatomic imaging.

For specific aim 2, study participants who remain eligible for pelvic radiation therapy (e.g. no distant metastases) will be subdivided into two cohorts: those without suspicious extraprostatic activity on PSMA-PET/MRI and those whose PSMA-PET/MRI demonstrates suspected seminal vesicle invasion and/or pelvic nodal metastatic disease. Those without suspicious extraprostatic uptake will undergo standard-of-care radiation therapy. Patients with positive PSMA-PET/MRI scans will undergo radiation treatment planning with a boost given to the suspicious lesions. The primary endpoint of specific aim 2 is to assess the number of patients with positive PSMA-PET/MRI scans where the radiation boost is feasible. We expect that the radiation treatment planning will be feasible in at least 90% of patients with positive PSMA-PET/MRI scans. A secondary endpoint is to compare the frequency of acute radiation toxicities between the cohorts. We expect that less than 15% of patients who undergo PSMA-PET/MRI directed LN radiotherapy boost will experience CTCAE v5.0 grade 3+ genitourinary or gastrointestinal toxicities and that no patient will experience a grade 5 genitourinary or gastrointestinal toxicity. All grade 3 toxicities will be reviewed by the radiation oncology sub-investigator. If any grade 4 or 5 events occur, the cases will be reviewed among members of the study team and the study will potentially be paused/terminated if there is concern that deviation from standard of care radiation therapy has caused undue harm to the patient.

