This clinical feasibility study will investigate the use of PSMA-PET/MRI to guide radiation treatment planning and delivery in patients with known or suspected locally metastatic prostate cancer at the time of diagnosis. The patients will undergo a single PSMA-PET/MRI (or PET/CT in some circumstances) prior to initiation of treatment. Following development of a PSMA-PET guided radiation treatment plan, therapeutic radiation will be delivered per standard-of-care parameters and assessments of feasibility and tolerability will be performed. A total of 10 patients will be enrolled in this study. If the PET/MRI demonstrates a suspicious finding that may make a patient ineligible for radiation therapy, the treating clinician (including urology and radiation oncology) will be alerted, and the decision to pursue biopsy and/or alter the patient's treatment plan will be based on standard of care imaging and consensus after presenting the case at the GU tumor board.

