6.4.6.3 PET/MRI Imaging Interpretation and Storage

Images from the PET/MRI will be stored and reviewed using a commercially available software package (MIM Encore, Cleveland, OH) and not be available for viewing in the institutional PACS or patient's medical record. This is in an effort to blind the treating physicians from making clinical decisions on an experimental imaging technique. The prostate MRI images will be sent to clinical PACS and the medical record as part of standard-of-care imaging and can be used in the clinical-decision making process. No formal interpretation will be generated for the $[^{68}\text{Ga}]$ PSMA-PET portion of the PET/MRI study, but the prostate MRI will have a clinical interpretation by a dedicated abdominal radiologist who will also be blinded to the patient enrollment in the study. Dedicated study readers from both abdominal imaging and molecular imaging will interpret first the prostate MRI alone, and then the fused PET/MRI to assess potential added value from the PET/MRI. The study readers will be blinded to the results of any additional standard-of-care

imaging and clinical evaluation and will only have knowledge that the patient has biopsy-proven prostate cancer.

Assessment of the prostate MR primary lesion location, extracapsular extension (ECE), seminal vesicle invasion (SVI), and metastatic disease will be evaluated utilizing a Likert scale from 1-5 to indicate reader confidence utilizing PI-RADS v2.0 criteria. The PSMA-PET/MRI will be evaluated with the same 1-5 Likert scale utilizing the PSMA-RADS v1.0 criteria.[16] The number of pelvic nodal metastases detected at each lymph node station will be recorded. Exams will be interpreted by three radiologists/nuclear medicine physicians to evaluate interreader agreement with disputes resolved by consensus.

MRI Data Analysis: The MRI images will be qualitatively analyzed.

Qualitative analysis: A visual evaluation of the pelvic lymph nodes with suspected metastatic disease will be performed. The number of positive metastatic lymph nodes and their nodal stations will be recorded. Nodal stations that will be examined include right and left common iliac, internal iliac, external iliac, obturator, inguinal, and retroperitoneal (total of 11 stations per patients).

MRI Images

- 1 = Normal lymph nodes
- 2 = Mild prominence not meeting RECIST criteria for adenopathy (low suspicion)
- 3 = Borderline enlarged by RECIST criteria (intermediate suspicion)

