PSMA-RADS-3B	Equivocal uptake in bone lesion not definitive but also not atypical of PCa on anatomic imaging (i.e., pure marrow-based lesion with little if any surrounding bony reaction, lytic or infiltrative lesion, or classic osteoblastic lesion). Comparison to bone scan, Na^{18}F PET, or tumor-protocol MR images may be helpful, and bone biopsy may have a role. Alternatively, follow-up imaging (either anatomic or PSMA-targeted PET/CT) with evidence of progression may confirm diagnosis. We recommend initial follow-up period of 3–6 mo.
PSMA-RADS-3C	Intense uptake in site highly atypical of all but advanced stages of PCa. Likelihood of nonprostatic malignancy or other benign tumor is high. Biopsy to confirm diagnosis histologically is often preferred, although organ-specific follow-up imaging may be done (e.g., liver-protocol MRI to evaluate possible primary hepatocellular carcinoma).
PSMA-RADS-3D	Lesion suggestive of malignancy on anatomic imaging but lacking uptake. Differential considerations include nonprostatic malignancy, neuroendocrine PCa, and an uncommon case of prostate adenocarcinoma that fails to express PSMA. Biopsy to confirm diagnosis histologically is often preferred, although organ-specific follow-up imaging may be done.
PSMA-RADS-4 (PCa highly likely)	Intense uptake in site typical of PCa but lacking definitive findings on conventional imaging. Given the high specificity of PSMA agents in all reported series, it is unlikely that biopsy confirmation will be needed, although obtaining tissue for genomic analysis or other purposes may be useful.
PSMA-RADS-5 (PCa almost certainly present)	Intense uptake in site typical of PCa and having corresponding findings on conventional imaging. Given the high specificity of PSMA agents in all reported series, it is unlikely that biopsy confirmation will be needed, although obtaining tissue for genomic analysis or other purposes may be useful.

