6.6.3 Analysis

Demographic and clinical characteristics of all the enrolled patients will be summarized using descriptive and graphical statistics. Mean and standard deviation will be provided for continuous variable and counts and percentage will be for categorical variables. To ensure the quality of imaging data, imaging data from three readers will be assessed first using Kappa statistics (K) for inter-rater agreement.

For the primary analysis in Aim 1, the number of patients who are identified with lymph node metastases (positive nodal) will be counted, and percentage and 95% exact confidence interval will be calculated using the Clopper-Pearson method for PSMA-PET/MRI and MRI respectively.

Concordance and agreement between two methods will be evaluated using Cohen's kappa statistic, κ . For the primary analysis in Aim 2, SUV thresholding, CTV, and other imaging parameters between PSMA-PET/MRI and MRI will be determined using the Bland-Altman plot analysis in addition to descriptive analysis. Safety analysis of acute radiation toxicities related AE/SAE in Aim 2 will be descriptive, such as frequency and percentage will be reported. We will also report the frequency of patients with any grade 3 GI or GU toxicity, and any grade 4-5 toxicity. All statistical analysis will be carried out using the Statistical Analysis Software SAS v 9.4.

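### Seminal vesicle confidence is to be compared on a 0-3 scale that no reader is told to use; the 1-5 scores that are collected can be compared but have different anchors for MRI and PET/MRI

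*Combined protocol and SAP*

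**What the plan says.** Section 6.5.5 (Study Variables and Key Endpoints) lists this among the Aim 1 comparisons: "The confidence in detection of seminal vesicle invasion on a 0-3 Likert scale will also be compared between MRI and PSMA-PET/MRI". It gives no meaning for the levels 0, 1, 2 and 3.

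Section 6.4.6.3 (PET/MRI Imaging Interpretation and Storage) describes the scoring. For the prostate MRI, the list of features to be scored includes this: "seminal vesicle invasion (SVI), and metastatic disease will be evaluated utilizing a Likert scale from 1-5 to indicate reader confidence utilizing PI-RADS v2.0 criteria". For the fused study: "The PSMA-PET/MRI will be evaluated with the same 1-5 Likert scale utilizing the PSMA-RADS v1.0 criteria". Study readers score the MRI alone first and then the fused images. Three readers take part, and disputes go to consensus.

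Table 1 in the same section sets out PSMA-RADS v1.0. Category 4 reads "Intense uptake in site typical of PCa but lacking definitive findings on conventional imaging" and category 5 reads "Intense uptake in site typical of PCa and having corresponding findings on conventional imaging".

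Section 6.6.3 (Analysis) says "Concordance and agreement between two methods will be evaluated using" Cohen's kappa. It names no analysis for the seminal vesicle confidence score. Section 6.0 gives the size of the study: "A total of 10 patients will be enrolled in this study".

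**The concern.** An endpoint should be a function of data that the plan collects. Here the endpoint section names a four-level score and the reading section collects a five-level one. Someone writing the analysis program must choose among three courses: treat 0-3 as a slip, collapse the five levels to four, or look for a separate field that the plan does not describe. These need not give the same answer.

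Correcting the number alone leaves a second difficulty. A confidence comparison has meaning only if a given score means the same thing on both reads. The two reads share the numerals 1 to 5 but are tied to different criteria. A shift in score could therefore reflect the change of criteria rather than a change in how sure the reader is that the seminal vesicles are invaded. Added confidence from PET is what this comparison is meant to show.

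**Working it through.** The plan states no figure to reproduce here: section 6.6.1 gives no power or sample size calculation. The check is a comparison of texts, followed by a small count.

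**1. The scales side by side**

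| | Section 6.5.5 | 6.4.6.3, MRI alone | 6.4.6.3, fused PET/MRI |
|---|---|---|---|
| Range | 0-3 | 1-5 | 1-5 |
| Levels | 4 | 5 | 5 |
| Criteria | none given | PI-RADS v2.0 | PSMA-RADS v1.0 |
| Written anchors for seminal vesicle invasion | none | none | none |

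Section 6.4.6.3 does give five worded MRI levels, but they describe lymph nodes. Table 1 speaks of soft-tissue sites, nodes and bone, and has no seminal vesicle entry.

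**2. Does a 1-5 score determine a 0-3 score?** Count the recodings that keep the order.

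- All order-preserving maps from five levels into four: C(5 + 4 − 1, 5) = C(8, 5) = 56.
- Those that use all four target levels: choose 3 cut points from the 4 gaps between adjacent scores, C(4, 3) = 4. Each merges one adjacent pair.

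The plan selects none of them, so the 0-3 result does not follow from the 1-5 scores.

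**3. Can the choice change the result?** The data below are an assumption made for illustration, not trial data. Ten patients have MRI scores 1,1,2,2,2,3,3,4,4,5 and fused scores 1,2,1,2,3,4,3,5,5,5. Unweighted kappa = (observed − chance agreement) / (1 − chance agreement).

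| Scale used | Observed | Chance | Kappa | Mean difference | Up / down |
|---|---|---|---|---|---|
| 1-5 as collected | 0.40 | 0.19 | 0.21/0.81 = 0.26 | 0.4 | 5 / 1 |
| 0-3, merge 1 and 2 | 0.60 | 0.29 | 0.31/0.71 = 0.44 | 0.4 | 4 / 0 |
| 0-3, merge 2 and 3 | 0.50 | 0.29 | 0.21/0.71 = 0.30 | 0.3 | 4 / 1 |
| 0-3, merge 3 and 4 | 0.50 | 0.25 | 0.25/0.75 = 0.33 | 0.3 | 4 / 1 |
| 0-3, merge 4 and 5 | 0.60 | 0.26 | 0.34/0.74 = 0.46 | 0.2 | 3 / 1 |

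On the same reads, kappa runs from 0.30 to 0.46 across the four recodings, and the mean difference from 0.2 to 0.4. This shows only that the choice can matter. It does not predict the size of the effect in this trial.

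**4. Is the 1-5 comparison sound once the number is corrected?** It can be computed, since both reads yield a 1-5 score. Its meaning is the difficulty. Categories 4 and 5 of Table 1 both require intense uptake at a typical site, and what separates them is a correlate on conventional imaging. Study readers are blinded to other standard-of-care imaging, so the anatomic images in front of them are the study MRI. If that MRI is taken as the correlate (the plan does not say), two patients with identical intense uptake would score 4 or 5 according to the MRI finding alone. A focus not seen on MRI, which is where PET would add most, could not reach 5. The fused score would then depend partly on the score it is compared with. Category 3 is not a plain midpoint either: it holds both intense uptake at a highly atypical site (3C) and an anatomic lesion with no uptake (3D).

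**The case against.** The best defence is that 0-3 is a simple slip. Section 6.4.6.3 says that both reads use the same 1-5 scale and ties the MRI score to reader confidence. Change the numeral in 6.5.5 and the contradiction goes, with no recoding and no merged levels. Scoring each modality by its own published criteria may also be deliberate in a study of added value. And because Table 1 is applied in the text to pelvic nodes, its effect on a seminal vesicle score is an inference.

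Much of this stands. The plan does not announce a recoding, and one chosen after the reads is only a possibility. The defence does not remove the mismatch of anchors, however. If Table 1 is used for the seminal vesicles, the 4-to-5 step is not confidence alone; if it is not used, the fused score has no stated anchors.

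A reader might infer more than the documents support:

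- **That the comparison cannot be computed.** A paired 1-5 comparison can be.
- **That the Aim 2 cohorts are affected.** Section 6.5.5 assigns them by suspected invasion on PSMA-PET/MRI, not by a 0-3 score or a difference between reads. The absence of a cut-off for suspected invasion is a separate gap.
- **That positive/negative concordance for invasion is affected by the 4-to-5 step.** Section 6.5.5 lists that concordance separately. If 4 and 5 both count as positive, a move between them leaves it unchanged.
- **That all 10 patients are affected.** Section 6.4.6.2 allows PET/CT in place of PET/MRI, and such patients may have no MRI-alone and fused pair.

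**Conclusion.** The point holds in a limited form. Sections 6.5.5 and 6.4.6.3 give different scales for the same quantity, and nothing in the document connects them, so the stated comparison is not uniquely defined. Its 1-5 version can be computed but cannot be read cleanly as a difference in confidence.

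At most 10 patients and three readers are involved. The comparison is labelled neither primary nor secondary. The Aim 1 primary endpoint is nodal, the Aim 2 primary endpoint is feasibility of the boost, and neither depends on the 0-3 score. It should be corrected because the correction is cheap and the comparison is otherwise open to choice, but it does not threaten the main results.

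The conclusion assumes that no reading form outside these documents already defines a 0-3 field with common anchors. If one exists, it needs only to be written into the plan.

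**What to change.** - **Section 6.4.6.3:** add one five-point confidence scale for seminal vesicle invasion, with the same verbal anchors for the MRI-alone and fused reads, from 1 = definitely absent to 5 = definitely present.
- **Section 6.5.5:** replace 0-3 with that scale.
- **Section 6.6.3:** name a paired, descriptive summary for patients who have both reads, for example a cross-tabulation of MRI-alone against fused score with the numbers rising, unchanged and falling. State whether consensus or individual reader scores are used. No test is needed at this sample size.
- **PI-RADS v2.0 and PSMA-RADS v1.0:** keep these as separate descriptive fields, so that nothing already planned is lost.

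The cost is wording in these sections and one field on the reading form, handled as an amendment under section 6.7.3. No patient or scan is added. It is best done before the first read. If reads have already taken place, the field would have to be scored again from the stored images.

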6.2 Study Objectives

Specific Aim #1: Determine the concordance of imaging findings for PSMA-PET/MRI and MRI of the pelvis and prostate gland.

Hypothesis #1: PSMA-PET/MRI will identify more regional lymph node metastases than MRI alone.

There have been numerous prior studies demonstrating the value of MRI for the locoregional staging for PCa. We expect the simultaneous acquisition of MRI and PSMA PET data to provide valuable preoperative staging information, with PSMA PET detecting metastatic disease in subcentimeter pelvic lymph nodes not identified with MRI alone. Additionally, PSMA-PET/MRI provides whole body staging in regions not evaluated by pelvic MRI and may detect additional distant metastases.

Specific Aim #2: Establish feasibility and assess acute toxicity of PSMA-PET/MRI directed pelvic radiotherapy.

Hypothesis #2: PSMA-PET/MRI directed radiation therapy will be feasible in the vast majority of patients (>90%) and can be safely administered without increased acute radiation toxicities.

The primary goal of Specific Aim 2 is to provide preliminary information to confirm the feasibility of radiation dose escalation to the suspicious LNs identified on PSMA-PET/MRI. If results from this trial are supportive, this will lead to a larger clinical trial evaluating efficacy and disease outcomes between patients who have undergone PSMA-PET/MRI directed radiotherapy versus standard-of-care pelvic radiotherapy.

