6.5.2 RADIOTHERAPY TARGET VOLUME DELINEATION (Figure 1)

Varian Eclipse software (Varian Medical Systems LLC, Palo Alto, CA, USA) will be used for radiotherapy target delineation and treatment planning. For all patients we will initially define traditional standard-of-care clinical target volumes for the treatment of high risk prostate cancer:

CTV_{P+SV} will contain the entire prostate gland and portion of the seminal vesicles at risk for tumor involvement. At least the proximal 1cm of the seminal vesicles. In cases where gross seminal vesicle invasion is identified the entire seminal vesicles will be included.

CTV_{eLN} will contain the elective lymph node target volumes. Elective nodal regions will be delineated in accordance with published consensus guidelines⁷ and will include the obturator, internal iliac, external iliac, and distal common iliac chains.

Next, the PSMA PET scan will be rigidly co-registered to radiation simulation CT scan. Rigid co-registration is preferred for two specific reasons: (1) we recognize that 8-10 weeks of androgen suppression between PSMA-PET/MRI and radiotherapy simulation may lead to changes in LN size that may lead to error in deformable registration, and (2) prior experience with PSMA-PET/MRI co-

[figure not shown]

Figure 1: Example of fluciclovine-PET/MRI directed radiotherapy treatment planning. Left image shows the $[^{18}\text{F}]$ fluciclovine PET-MRI with lower window of PET window set to 1.3 times blood pool. The suspicious LN is segmented in red. Right image is the treatment planning CT for the same patient with $\text{CTV}_{\text{LN BOOST}}$ delineated in green and the associated PTV in blue.

registration in the biochemical recurrence setting indicates that rigid co-registration results in good anatomic agreement in the majority of cases⁸. Using the registered PSMA-PET/MRI we will delineate an additional CTV:

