$\text{CTV}_{\text{LN BOOST}}$ will contain LNs with maximum SUV greater than 1.3 times the blood pool reference. The LNs will be segmented on the MRI portion of the PSMA-PET/MRI and superimposed on the co-registered CT simulation scan. The resulting structure will be edited to create $\text{CTV}_{\text{LN BOOST}}$ by excluding bowel structures and barriers to tumor spread (e.g. muscle or bone). We note that suspicious LNs are likely to be smaller on the CT simulation scan due to the initiation of androgen suppression, but $\text{CTV}_{\text{LN BOOST}}$ will not be further reduced so as to account for potential microscopic tumor extension. This concept is analogous to involved node radiotherapy utilized for post-chemotherapy consolidation of lymphoma⁹.

Planning target volume (PTV) expansions for $\text{CTV}_{\text{P+SV}}$ will be 4mm posteriorly and 7mm in all other directions. PTV expansions for CTV_{eLN} and $\text{CTV}_{\text{LN BOOST}}$ will be 8mm in all directions.

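### Aim 2 counts patients with seminal vesicle invasion alone in the boost-feasibility denominator and the boosted toxicity cohort, but the plan defines a PET-directed boost only for lymph nodes

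*Combined protocol and SAP*

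**What the plan says.** Section 6.5.5 divides patients who remain eligible for pelvic radiotherapy into two cohorts: those with no suspicious extraprostatic activity, and "those whose PSMA-PET/MRI demonstrates suspected seminal vesicle invasion and/or pelvic nodal metastatic disease". It then states: "Patients with positive PSMA-PET/MRI scans will undergo radiation treatment planning with a boost given to the suspicious lesions". The Aim 2 primary endpoint is to "assess the number of patients with positive PSMA-PET/MRI scans where the radiation boost is feasible", with an expectation of at least 90%. A secondary endpoint compares acute toxicity between the two cohorts. A separate expectation, under 15% with grade 3 or higher genitourinary or gastrointestinal toxicity, is confined to patients who receive the nodal boost.

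Section 6.2 gives the primary goal of Aim 2 as to "confirm the feasibility of radiation dose escalation to the suspicious LNs identified on PSMA-PET/MRI".

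Section 6.5.2 starts with the standard volumes: "For all patients we will initially define traditional standard-of-care clinical target volumes". One of these covers the prostate and at least the proximal 1 cm of the seminal vesicles, with this extension: "In cases where gross seminal vesicle invasion is identified the entire seminal vesicles will be included". It does not say which imaging identifies the invasion. The PET is registered afterwards: "Using the registered PSMA-PET/MRI we will delineate an additional CTV". That volume contains "LNs with maximum SUV greater than 1.3 times the blood pool reference". Section 6.5.3 prescribes 70 Gy to the prostate and seminal vesicle volume, 60.2 Gy to the nodal boost and 50.4 Gy to the elective nodes.

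**The concern.** The group that is counted and the group that can be boosted differ. The and/or in section 6.5.5 admits a man with suspected SVI and no suspicious node. He enters a denominator meant to show whether a boost can be planned, yet sections 6.5.2 and 6.5.3 give him no PET-directed boost volume or dose, and the boost row of Table 2 has no structure to apply to.

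Two results are exposed. The feasibility proportion mixes patients who test the nodal boost with patients who do not, and its direction of error depends on a scoring rule that is not written and could be settled after the results are known. The toxicity comparison places men without a nodal boost in the cohort meant to represent boosted men. Section 6.2 says supportive results will lead to a larger trial, so the reported figures should describe the treatment that trial would study.

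**Working it through.** **Inputs.** Total enrolment is 10 (sections 6.0 and 6.3.1). Section 6.6.1 states that no power or sample size calculation was done, so there is no figure of that kind to reproduce. The dose schedule in 6.5.3 is consistent: 28 × 2.5 = 70, 28 × 2.15 = 60.2 and 28 × 1.8 = 50.4 Gy. The documents give no expected count of nodal or SVI-only patients. Let n be patients with a boost-eligible node and s be SVI-only patients. Both are assumed, with n + s at most 10.

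**Step 1: the texts side by side.**

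| Item | Nodal disease | SVI only |
|---|---|---|
| In the positive cohort (6.5.5) | yes | yes |
| Additional volume drawn from the PET (6.5.2) | yes | no |
| PET-directed boost dose (6.5.3) | 60.2 Gy, up to 70 Gy | none |
| Boost row in Table 2 applies | yes | no |
| Seminal vesicles in the 70 Gy standard volume | yes | yes |

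The word positive is not formally defined. Reading it as the second cohort is the natural reading of 6.5.5.

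**Step 2: SVI-only patients scored feasible, one nodal plan not feasible.** The nodal proportion is (n − 1)/n. The proportion under 6.5.5 is (n − 1 + s)/(n + s).

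| n | Nodal only | s = 1 | s = 2 |
|---|---|---|---|
| 3 | 2/3 = 66.7% | 3/4 = 75.0% | 4/5 = 80.0% |
| 4 | 3/4 = 75.0% | 4/5 = 80.0% | 5/6 = 83.3% |
| 6 | 5/6 = 83.3% | 6/7 = 85.7% | 7/8 = 87.5% |
| 8 | 7/8 = 87.5% | 8/9 = 88.9% | 9/10 = 90.0% |
| 9 | 8/9 = 88.9% | 9/10 = 90.0% | exceeds 10 patients |

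The first SVI-only patient adds n/(n + 1) − (n − 1)/n = 1/[n(n + 1)]. That is 1/12 = 8.3 points at n = 3, falling to 1/90 = 1.1 points at n = 9. With one failure the proportion reaches 90% only when the denominator is 10, that is, when every enrolled patient is positive.

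**Step 3: SVI-only patients scored not feasible, every nodal plan feasible, s = 1.** The nodal proportion is 100%. The proportion under 6.5.5 is n/(n + 1): 80.0% (n = 4), 85.7% (n = 6) or 88.9% (n = 8).

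**Step 4: one data set under each rule.** Take six positive patients, two of them SVI-only, and one nodal failure. Nodal patients alone give 3/4 = 75.0%. Scoring the SVI-only men feasible gives 5/6 = 83.3%, and scoring them not feasible gives 3/6 = 50.0%.

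**Step 5: precision.** Section 6.6.3 names the Clopper-Pearson interval for Aim 1 and gives none for feasibility. Using it here, the 95% limits are 19.4–99.4% for 3/4, 35.9–99.6% for 5/6 and 47.3–99.7% for 7/8. They overlap heavily.

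**Step 6: toxicity.** Let p1 be the rate with a nodal boost and p0 the rate without, and assume SVI-only men have rate p0. The expected positive-cohort rate is (n·p1 + s·p0)/(n + s), so the expected difference from the PET-negative cohort is (p1 − p0) × n/(n + s). The fraction of the true difference retained is 80.0% for (n, s) = (4, 1), 66.7% for (4, 2), 85.7% for (6, 1), 75.0% for (6, 2) and 88.9% for (8, 1).

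**The case against.** The best reply is that an SVI-only man is still a test of PET-directed treatment. Section 6.5.2 extends the target to the whole seminal vesicles when gross invasion is identified and names no imaging source, so PET may trigger the extension. That volume receives 70 Gy, more than the 60.2 Gy nodal prescription, and 6.5.3 describes the institutional technique as an integrated boost to the prostate and proximal seminal vesicles. Table 2 sets coverage, rectal and bladder criteria that his plan must meet. The title of Aim 2 and Hypothesis 2 also speak of PET-directed radiotherapy in general.

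Part of this stands. A reader might infer that an SVI-only man is an automatic success, or that he receives nothing extra. The documents support neither: his plan still faces real dosimetric criteria, and he may have more seminal vesicle treated. But the extension is a rule within a standard-of-care volume drawn for all patients, so meeting it says nothing about the nodal dose escalation that 6.2 names as the primary goal.

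It is also fair that eligibility favours nodal disease (suspected pelvic metastases or nodal risk of at least 20%), so s may be small or zero. And the cohorts are split by disease extent without randomisation, so the toxicity comparison is confounded whatever is done here.

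**Conclusion.** The mismatch between 6.5.5 and 6.5.2–6.5.3 is real and affects the Aim 2 primary endpoint and the cohort toxicity comparison. Its size is modest and unknown. Under assumed counts, with one nodal failure and SVI-only men scored feasible, each such man moves the feasibility estimate by roughly 1 to 8 points for 3 to 9 nodal patients. The other scoring moves it downwards. The dilution of the toxicity contrast further assumes that SVI-only men have the unboosted rate. If whole-vesicle treatment changes toxicity, the distortion could differ.

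Three stronger conclusions might be inferred, and the documents support none of them. First, the mismatch does not overturn a go/no-go decision: the 90% figure is an expectation, there is no test or decision rule, and safety reporting is descriptive. Second, it does not bias the 15% toxicity expectation, which 6.5.5 already defines on patients who undergo the nodal boost. Third, section 6.4.6.3, which keeps PET images from treating physicians, should not be read as forbidding PET-based contouring: sections 6.0 and 6.5.2–6.5.5 plainly direct it.

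The change is worth making before reporting because it is nearly free and removes a scoring choice that could otherwise be made after the data are seen.

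**What to change.** In section 6.5.5, define the Aim 2 feasibility denominator as patients who remain eligible for pelvic radiotherapy, whose PSMA-PET/MRI is positive for pelvic nodal disease, and who have at least one node meeting the 6.5.2 boost rule. Count them whether or not the boost is finally planned or delivered, so that failures stay in. Men with both nodal disease and SVI belong here. Requiring a positive nodal read as well as the uptake rule keeps out a man whose scan is read as negative, whom 6.5.5 sends to standard radiotherapy.

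Report SVI-only patients as a separate group for feasibility. Tabulate acute toxicity in three rows: nodal boost delivered, SVI-only, and PET-negative. The separate SVI-only row keeps men who may have had whole-vesicle treatment out of the comparator. List each planned nodal boost that was not delivered, with the reason.

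The cost is amendment wording and one extra table row, with no new scans or visits and no change to a clinical threshold. The downside is a smaller denominator and a wider interval: with one failure, 35.9–99.6% for six patients against 47.3–99.7% for eight.
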